4.1.7 Replacement of Subjects

Subjects who withdraw from the study will be replaced where possible. A maximum number of five subjects may be replaced.

4.1.8 Withdrawal of Informed Consent for Data and Biological Samples

Biological Samples Obtained for the Main Study

Study data are protected by the use of a SID number, which is a number specific to the subject. The investigator is in control of the information that is needed to connect a study sample to a subject. A subject's consent to the use of data does not have a specific expiration date, but the subject may withdraw consent at any time by notifying the investigator. If consent is withdrawn, any samples collected prior to that time may still be given to and used by the sponsor but no new data or samples will be collected unless specifically required to monitor safety of the subject (Section 10.6).

Plasma and Muscle Biopsy Samples Obtained for Genetic Research or Future Non-genetic Research

Samples obtained for genetic research or future non-genetic research will be labelled with a sample identification number linked to the SID number but will not be labelled with personal identifiers such as the subject's name (Section 10.7). If the subject withdraws consent for participating in the genetic research or future non-genetic research, the sponsor will locate the

subject's sample and destroy it. The coding of samples and results is to ensure that these research results are kept confidential by keeping the subject's identity and these results separate.

If the subject consents to have his/her samples used for genetic research or future non-genetic research, this additional research may not start immediately and may start at any time during the storage period. The subject's sample(s) including any specimens of extracted deoxyribonucleic acid (DNA) will be stored by the sponsor with similar samples from other subjects at a secure central laboratory. The subject's samples will not be kept for more than 15 years after the end of the study in which they were collected. If the subject chooses not to allow his/her study samples to be used for genetic research or future non-genetic research, the samples will be destroyed by the sponsor once they are no longer required for the main study.

If consent is withdrawn after a sample has been taken but before the subject's sample is sent to the sponsor for genetic research or future non-genetic research, the investigator will arrange to have it destroyed. If consent is withdrawn after the subject's sample(s) have been sent to the sponsor for genetic research or future non-genetic research, the sponsor and the investigator will ensure that these sample(s) are destroyed unless the sample identification number has been removed and the subject can no longer be linked to any sample(s). However, if the subject's samples have already been used for research, the sponsor is not required to destroy results of this research. In this case only the remaining sample(s) will be destroyed.

4.2 Schedule of Study Procedures

4.2.1 Enrolment/Screening Period

Table 5 shows all procedures to be conducted at the screening visit.

Table 5 Schedule of Screening Procedures

Study Period	Screening
Visit Number	V1
Procedure / Study Day	Day -28 to Day -1
Written informed consent/ assignment of SID number	X
Optional informed consent for blood samples for future genetic research ^a	X
Optional informed consent for blood samples for future non-genetic research ^a	X
Medical history, including smoking and alcohol history	X
Physical examination (full) including structured neurological examination ^b	X
Verify eligibility criteria	X
Weight, height and BMI calculation	X

Study Period	Screening
Visit Number	V1
Procedure / Study Day	Day -28 to Day -1
Demographics	X
12-lead ECG ^c	X
Vital signs (BP ^d , pulse, body temperature, respiration rate)	X
Alcohol breath test	X
Collect blood for:	
LFTs, Cr and eGFR calculation only	X
TSH	X
HbA1c	X
Calcitonin	X
...Pancreatic lipase and amylase	X
HIV-1 and -2 antibodies; hepatitis B and C serology	X
Serum pregnancy test	X
Collect urine for:	
Urine drug screen	X
Urine pregnancy test if applicable	X
SC injection self-administration training ^e	X
Advise on washout of second non-metformin diabetes therapy if applicable ^f	X
Assessment of AEs and SAEs ^g	X
Concomitant medications	X

AE = adverse event; BMI = body mass index, BP = blood pressure, Cr = creatinine, DPP4 = dipeptidyl peptidase 4 inhibitor; ECG = electrocardiogram, eGFR = estimated glomerular filtration rate, FBC = full blood count, HbA1c = glycated haemoglobin, HIV = human immunodeficiency virus, LFTs = liver function tests (albumin, alanine transaminase [ALT], aspartate aminotransferase [AST], alkaline phosphatase [ALP] and total bilirubin), SAE = serious adverse event; SC = subcutaneous; SGLT2i = sodium-glucose co-transporter inhibitor(s); SID = subject identification, TSH = Thyroid stimulating hormone; V = Visit.

- ^a During the informed consent process subjects will be asked to provide consent for the main study as well as for the optional components: future genetic research and future non-genetic research. Only sample(s) for which the subject has consented will be taken.
- ^b Only the screening physical examination will be a full examination including a structured neurological examination. For all time points thereafter, only a targeted physical examination is required.
- ^c A single digital ECG recording should be performed after the subject has rested for 10 minutes.
- ^d Blood pressure should be measured once at heart level in the non-dominant group where possible, with the subject either seated or supine and rested for 10 minutes prior to the measurement.
- ^e Subject's ability to self-administer investigational product will be verified by using normal saline subcutaneous injections.
- ^f Once the subject's eligibility has been confirmed, subjects who take a second agent for their diabetes in addition to metformin (ie, a DPP4 inhibitor, SGLT2i, sulfonylurea, or glitinide), should be advised to stop the therapy 28 days before Visit 4.

^g AEs and SAEs will be assessed from the time informed consent form is signed.

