3.2.2 Rationale for Study Population

Subjects aged ≥ 30 and ≤ 75 years, with BMI > 28 and ≤ 40 kg/m² will be included in the study population to balance recruitment potential with projected variability in EE measurements. Conflicting reports exist with respect to the impact of obesity on EE (Carneiro et al 2016) and subjects with T2DM have differing REE and AEE, and this may be influenced by glycaemic control (Caron et al 2016). In view of this, subjects without poor glycaemic control (HbA1c $\leq 8.0\%$) using metformin, dipeptidyl peptidase-4 (DPP4) inhibitors, sodium-glucose co-transporter inhibitors (SGLT2i), sulfonylurea, or glitinide will be enrolled; if they are on dual therapy, the non-metformin therapy will be washed out 4 weeks prior to dosing of MEDI0382 (Visit 4). In addition, subjects that partake in high intensity exercise (and likely have a high BMI due to excess muscle bulk) will be excluded.

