4.2.2 Randomised Treatment Period

[Table 6](#) shows all procedures to be conducted during the treatment period.

Table 6 Treatment Period Study Procedures

Study Period	Placebo Period					Treatment Period					
Visit Number	V2	V3 (optional)	V4			V5	V6	V7	V8	V9	
Procedure / Study	Day -1	Day 1-14	Day 15	Day 16	Day 17	Day 21	Day 25	Day 32	Day 41 or 42	Day 58	Day 59
Admit to clinical unit			X							X	
Discharge from clinical unit					X						X
Outpatient visit to clinical unit	X	X				X	X	X	X		
Fasting on the night before required ^a	X	X	X	X	X			X	X	X	X
Physical examination (abbreviated)	X				X			X		X ^b	
Weight ^c	X				X			X			X
ECG					X						X
Vital signs (BP, pulse, body temperature, respiration rate) ^d	X				X			X			X
Collect Blood for											
Serum chemistry	X				X			X			X
Haematology	X				X			X			X
Pancreatic lipase and amylase					X			X			X
HbA1c					X						X
Serum calcitonin					X						X
Fasting lipid profile					X						X
Serum pregnancy test	X				X						
Optional for genetic testing	X										

Table 6 Treatment Period Study Procedures

Study Period	Placebo Period				Treatment Period						
Visit Number	V2	V3 (optional)	V4			V5	V6	V7	V8	V9	
Procedure / Study	Day -1	Day 1-14	Day 15	Day 16	Day 17	Day 21	Day 25	Day 32	Day 41 or 42	Day 58	Day 59
Optional non-genetic testing	X										X

██████████
					█			█			█

██████████
					█			█			█
Collect urine for:											
Urinalysis					X			X			X
Urine pregnancy test	X				X			X			X
Alcohol breath and urinary illicit drug test	X										
DLW assessment ^g	X				X				X	X	X
24-hour protein estimation			X							X	
DLW administration ^h	X								X		

██████████
		X							X		
Fixed standardised breakfast (Meal Type A) ^j	X			X				X			X

██
											

Table 6 Treatment Period Study Procedures

Study Period	Placebo Period				Treatment Period						
Visit Number	V2	V3 (optional)	V4			V5	V6	V7	V8	V9	
Procedure / Study	Day -1	Day 1-14	Day 15	Day 16	Day 17	Day 21	Day 25	Day 32	Day 41 or 42	Day 58	Day 59
SmartPill™ capsule administration to assess gastric emptying			X							X	
Fixed standardised meals (Meal Type B) ⁿ			X							X	
Advice on diet prior to whole room calorimetry (remote contact or during visit)		X (Day 4-11)							X		
Subject enters whole room calorimeter ^o			X							X	
Exercise sessions ^p			X							X	
Hunger/satiety questionnaires ^q			X							X	
DXA scan ^r	X										X
Optional muscle biopsy ^s		X							X		
Hood-based indirect calorimetry ^t	X		X	X	X			X		X	X

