Provision of activity monitor and device training	X										
Activity monitoring	Subjects will be expected to wear the activity monitoring device until the final study visit (V10)										
Activity monitoring device battery check/ charging (as required) ^u				X				X		X	
Weight measurement at home	Subjects will be expected to weigh themselves every 72 hours whilst at home										

Table 6 Treatment Period Study Procedures

Study Period	Placebo Period				Treatment Period						
Visit Number	V2	V3 (optional)	V4			V5	V6	V7	V8	V9	
Procedure / Study	Day -1	Day 1-14	Day 15	Day 16	Day 17	Day 21	Day 25	Day 32	Day 41 or 42	Day 58	Day 59
Glucose meter provision and device training	X										
Provision of paper diary or digital device for collection of capillary glucose and weight measurements	X										
Capillary glucose measurements	Subjects will be requested to measure pre-breakfast capillary plasma glucose measurements every 72 hours whilst at home and if they feel unwell or experience symptoms of hypoglycaemia until Visit 10										
Assessment of TEAEs/TESAEs ^v	Will be collected continuously throughout the study										
Concomitant medications	Will be collected continuously throughout the study										
Subcutaneous injection training	X										
Verify eligibility criteria	X										
Randomisation	X										
[REDACTED]	[REDACTED]										
[REDACTED]	[REDACTED]										
[REDACTED]	[REDACTED]										
[REDACTED]	[REDACTED]										
[REDACTED]	[REDACTED]										

ADA = anti-drug antibody; AE = adverse event; BP = blood pressure; DLW = doubly labelled water; DXA = dual X ray absorptiometry; ECG = electrocardiogram; eCRF = electronic case report form; GIP = glucose-dependent insulintropic polypeptide; GLP-1 = glucagon-like peptide-1; IVGTT = intravenous glucose tolerance test; LFT = liver function tests, min = minutes; MMTT = mixed-meal tolerance test; PK = pharmacokinetic(s); SAE = serious adverse event; TEAE = treatment-emergent adverse event; TESA = treatment-emergent serious adverse event; V = Visit; VAS = Visual Analog Scale.

- a Fasting for at least 12 hours is required the night before on Days -1, 15, 16, 17, 32, 58, and 59; on Day 17 subjects should be fasted overnight for at least 8 hours prior to investigational product administration and for a further 4 hours after investigational product administration as described in footnote s. For [REDACTED]
- b Physical exam on Day 58 can occur at any time on Day 58 or 59.

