- c Body weight should be measured in the morning prior to breakfast or any of the standardised meals (predose on Day17); the subject should take off their shoes and remove bulky clothing. Calibrated scales should be used.
- d Vital signs should be performed predose and 4 hours postdose on Day 17.
- e PK samples should be taken predose.
- f If possible, [REDACTED] See Section 4.3.7 for additional details.
- g Urine samples for doubly labelled water assessment should be taken at baseline (T = 0) prior to administration of the doubly labelled water and further samples should be collected at T = 2, 3 and 4 hours \pm 15 min afterwards and then a single sample should be taken 17 days \pm 4 hours later (eg, if DLW was given on Day -1 at 1000 hours, collection of urine would occur prior to 1000 hours and then at 2, 3, and 4 hours afterwards and then again on Day 17 at 1000 hours \pm 4 hours). Visit 8 may occur on either Day 41 or 42, and if more convenient, the subject may be provided with instructions to perform the urine collections themselves at home after administration of DLW at the specified time points. The subsequent follow-up urine sample should be 17 days later eg, if the DLW was administered on Day 42, the follow-up sample should be taken on Day 59.
- h DLW may be administered at any time.
- i [REDACTED]
- j A fixed standardised breakfast (as part of the MMTT) (Meal Type A) should be given to all subjects on Day -1 upon arrival to the study unit following the hood calorimetry assessment.
- k [REDACTED]
- l Ad libitum meal (Meal Type C) consumption will be measured in a single-blind fashion (see Section 4.3.2.2 for further details). The meal should commence at 1300 \pm 2 hour. Subjects will be requested to eat until they feel comfortably full and the meal duration should be flexible according to subject preference.
- m Subjects should be provided with a food diary after the ad libitum lunch on days -1, 16, 32 and 59 requested to record all food and drink they consume that day for the remainder of the day until midnight.

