4.2.3 Follow-up Period

Table 7 shows all procedures to be conducted during the follow-up period.

Table 7 Schedule of Follow-up Procedures

Study Period	Follow-up Period
Visit Number	Final Visit (V10)
Procedure / Study Day	28 days post last dose (\pm 3 days)
Physical examination (abbreviated)	X
Remove activity monitoring device	X
Weight	X
ECG	X
Vital signs (BP, pulse, body temperature, respiration rate) ^a	X
Serum chemistry panel	X
Calcitonin ^b	X
Haematology	X
Urinalysis	X
HbA1c	X
Urine pregnancy test	X
	
Assessment of TEAEs/TESAEs ^d	X
Concomitant medications ^e	X

ADA = anti-drug antibody; AE = adverse event; BP = blood pressure; ECG = electrocardiogram; HbA1c = glycated haemoglobin, SAE = serious adverse event; TEAE = treatment-emergent adverse event; TESAE = treatment-emergent serious adverse event; ULN = upper limit of normal; V = visit.

^a Blood pressure should be measured once at heart level in the non-dominant arm where possible, with the subject seated and rested for 10 minutes prior to the measurement.

^b Only to be repeated if the calcitonin level was > ULN in the sample taken at the end of dosing.

^c See Section 4.3.7 for details.

^d AEs and SAEs will be assessed from the time of signed informed consent form.

^e If a second non-metformin agent was washed out during the screening period the investigator and/or study team should consider whether it is appropriate to re-start this therapy.

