4.3.5 Clinical Laboratory Tests

A Laboratory Manual will be provided to the sites that specifies the procedures for collection, processing, storage, and shipment of samples, as well as laboratory contact information, specific to this clinical research study.

Clinical laboratory safety tests will be performed in a licensed central or licensed local clinical laboratory. Urine pregnancy tests may be performed at the site using a licensed test (dipstick). Abnormal laboratory results should be repeated as soon as possible (preferably within 24 to 48 hours).

The following clinical laboratory tests will be performed (refer to time points in the schedules of study procedures (Section 4.2):

Serum Chemistry

- | | |
|-------------|-------------------|
| • Potassium | • Total bilirubin |
| • Sodium | • Creatinine |
| • ALT | • Blood urea |
| • AST | • Albumin |
| • ALP | |

ALP = alkaline phosphatase; ALT = alanine transaminase; AST = aspartate transaminase.

Notes:

Liver function tests = AST, ALT, ALP, total bilirubin, and albumin

Tests for AST, ALT, ALP, and total bilirubin must be conducted concurrently and assessed concurrently.

Haematology

- White blood cell count with differential
- Red blood cell count
- Haematocrit
- Haemoglobin
- Platelet count
- Mean corpuscular volume
- Mean corpuscular haemoglobin concentration

Urinalysis

- Protein
- Glucose
- Blood
- Urine drug screen ^a
- Ketones

Notes:

Urinalysis for protein, glucose, ketones, and blood may be performed at the site using a licensed test (dipstick).

- ^a Illicit drug panel will test for the following drugs; amphetamines, barbituates, benzodiazepines, cocaine, opiates (morphine, heroin), methamphetamine, cannabinoids (marijuana), methadone, phencyclidine, methylenedioxymethamphetamine (ecstasy), propoxyphene, and tricyclic antidepressants. Subjects who use tricyclic antidepressants or benzodiazepines for an established clinical indication may be permitted to enter the study based upon the judgement of the investigator.

Additional Urine Samples

- Urine samples for DLW assessment
- 24-hour urine collection for protein assessment

Pregnancy Test (females of childbearing potential only)

- Serum human chorionic gonadotropin (hCG; screening if applicable, and Day -1 and 17 only)
- Urine hCG

Other Laboratory/Blood Tests

- Calcitonin
- Alcohol screening test (breath- or urine-based test)
- Pancreatic amylase and lipase
- Glycated haemoglobin
- Anti-drug antibodies (immunogenicity)

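### Dual-therapy subjects stop their second diabetes agent 11 to 13 days before any scheduled or study-meter glucose reading

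*Protocol*

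**What the plan says.** Table 5 footnote f (Protocol 4.2.1) tells subjects on a second agent that they "should be advised to stop the therapy 28 days before Visit 4". Section 3.2.2 ties the same interval to active dosing: "the non-metformin therapy will be washed out 4 weeks prior to dosing of MEDI0382 (Visit 4"). Table 7 footnote e (Section 4.2.3) confirms where this falls in the calendar: "If a second non-metformin agent was washed out during the screening period".

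The glucose-related procedures are scheduled as follows.

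- **Visit 1 (Table 5).** HbA1c is the only glycaemic measure. Chemistry is restricted to "LFTs, Cr and eGFR calculation only". No meter, device training or diary is listed.
- **Day -1 (Table 6).** Table 6 "shows all procedures to be conducted during the treatment period". The row "Glucose meter provision and device training" is marked under Day -1 only, as is diary provision. Home readings every 72 hours are a row of this table. Section 4.3.1 places a meal test with serial blood sampling on the same day.
- **Day 17 (Table 6).** HbA1c and urinalysis appear for the first time since screening. Section 4.3.5 puts glucose and ketones in the urinalysis; its serum chemistry list has no glucose.

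Section 4.3.5.1 says the meter is issued at the start of the study but names no visit.

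**The concern.** The withdrawal is imposed by the protocol, not by usual care, and Section 10.3 itself gives washout of an existing medication as an example of what may cause a protocol-related SAE. Section 1.6 undertakes to monitor every subject's glycaemic control throughout the study. Under the schedules, a dual-therapy subject spends the first part of the washout without a study meter and without a scheduled glucose test. Section 3.1.4.3 identifies suspected hyperglycaemia from symptoms or from capillary readings; before Day -1 only symptoms can be relied on.

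What is at stake is patient safety on a limited scale: a symptomless rise in glucose that no scheduled or study-meter reading would show before the day of randomisation. The weight endpoint and its analysis are not involved.

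**Working it through.** **Day numbering.** Table 6 footnote g gives doubly labelled water on Day -1 and takes the 17-day sample "and then at 2, 3, and 4 hours afterwards and then again on Day 17 at 1000 hours". Without a Day 0, Day -1 to Day 17 is 1 + 16 = 17 days, as the protocol states. With a Day 0 it would be 18. So there is no Day 0, and Day -1 to Day 15 is 1 + 14 = 15 days.

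**Length of the gap.** Gap = 28 minus the days from Day -1 to the anchor day in Visit 4.

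| Anchor | Day -1 to anchor | Gap before Day -1 | Stop day | Share of washout |
|---|---|---|---|---|
| Day 15 (start of Visit 4) | 15 | 28 - 15 = 13 days | Day -14 | 13/28 = 46% |
| Day 17 (first MEDI0382 dose) | 17 | 28 - 17 = 11 days | Day -12 | 11/28 = 39% |

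**Other glycaemic measures.**

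- Screening HbA1c comes at or before the stop. Visit 1 can be as early as Day -28, so HbA1c precedes the stop by 0 to 14 days (28 - 14) or 0 to 16 days (28 - 12).
- The next HbA1c and urinalysis, on Day 17, come 13 + 17 = 30 or 11 + 17 = 28 days after the stop.
- Neither fills the gap, so the Day -1 meal test is the first scheduled glucose after the stop.

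**Effect of starting the existing 72-hour readings at the stop.** Take the first reading 72 hours after the stop.

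| | Stop Day -14 | Stop Day -12 |
|---|---|---|
| Readings before Day -1 | Days -11, -8, -5, -2 (4) | Days -9, -6, -3 (3) |
| First reading ahead of Day -1 | 13 - 3 = 10 days | 11 - 3 = 8 days |
| Third reading (washout day 9) ahead of Day -1 | 13 - 9 = 4 days | 11 - 9 = 2 days |
| Longest interval without a scheduled reading, now / changed | 13 / 3 days | 11 / 3 days |

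Three consecutive readings span 6 days, so they can meet the Section 3.1.4.3 example of three capillary values above 14 mmol/L in a week. A sustained rise that begins after the stop would be seen 2 to 4 days before Day -1. If a stop-day reading is added and is already above 14 mmol/L, the third reading falls on washout day 6, which is 11 - 6 = 5 or 13 - 6 = 7 days before Day -1.

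**The case against.** The strongest objection is that the gain is small. A single high value 8 to 10 days early does not meet the three-reading criterion, and a sustained rise is seen only 2 to 4 days sooner. Section 3.1.4.3 then asks for two laboratory fasting values more than 3 days apart before rescue is considered. With the Day 17 anchor, a first laboratory sample on Day -3 allows the second on Day 2; starting from the Day -1 meal test, it would be Day 4. That is 2 days gained, or 4 with the Day 15 anchor. This stands, and it is why the point is modest.

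Safeguards also exist. AEs are collected from consent, sites are to meter-test suspected cases (4.3.5.1), unscheduled visits with blood tests are allowed (4.2.4), and eligibility is checked again on Day -1. All but the last need a symptom or a suspicion first. The Day -1 check sets no glucose limit: the HbA1c criterion applies at screening, exclusion 7 concerns symptoms, and a symptomless rise is left to judgement under exclusion 1.

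The wording of 4.3.5.1 could be read as issue at consent, since Section 4.1.4 starts participation there. Table 6 is more specific and Table 5 lists no meter. If issue at screening was intended, the tables still need the same edit.

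Finally, Amendment 2 revised the hyperglycaemia section and both schedules at the regulator's request and left meter issue on Day -1, and parts of Section 1.6 are redacted. A rationale may exist that cannot be seen. Neither fact puts a reading into the interval.

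**Conclusion.** The concern holds. Followed as written, the protocol leaves 11 to 13 of the 28 washout days (39% to 46%) without a scheduled or study-meter glucose reading for every dual-therapy subject. This rests on there being no Day 0, which the protocol's own 17-day interval establishes, and on Table 6 governing when the meter is issued. The range reflects the two possible anchors.

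These percentages count days without a reading; they do not measure risk. The documents do not say how many subjects will be on dual therapy (anywhere from 0 to all 24 planned), nor how many would exceed 14 mmol/L after stopping one agent, so expected harm cannot be sized. The entry HbA1c limit, continued metformin, the exclusions and the Day -1 meal test all keep the risk low. This is a change that should be made because it is cheap and the protocol imposes the withdrawal; it does not threaten the trial's validity.

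**What to change.** For dual-therapy subjects only:

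1. Add the existing meter, training and diary rows to Table 5 at Visit 1, beside the washout advice. No scheduled visit lies between that advice and Day -1, so Visit 1 is the practical point of issue.
2. State which Visit 4 day anchors the 28 days, and require Visit 1 on or before the resulting stop day (Day -14 or Day -12).
3. Start the existing 72-hour and symptom-driven capillary readings when the agent is stopped.
4. Add one sentence: three readings above 14 mmol/L in one week before Day -1 prompt contact with the investigator and a laboratory fasting glucose at an unscheduled visit (4.2.4). The investigator then judges whether to randomise (exclusions 1 and 7) or resume the second agent.

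All other subjects keep the Day -1 issue.

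The cost is amendment wording and any approvals under Section 7.4, and 3 to 5 more finger-pricks per dual-therapy subject (3 or 4, plus one if a stop-day reading is taken). Some meters and diaries will go to subjects who then fail screening, because Visit 1 precedes confirmed eligibility. An extra visit with a laboratory test is needed only for subjects who trigger the prompt.
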